1.0 Specific Aims

To evaluate the efficacy of hydroxychloroquine as a treatment for hidradenitis suppurativa (HS)
We will conduct a pilot trial of standard dosing of hydroxychloroquine in patients with HS

To identify biomarkers as possible therapeutic targets for the treatment of HS
We will evaluate the levels of inflammatory cytokines in the peripheral blood of patients with HS.

2.0 Background information

Hidradenitis suppurativa is a debilitating and mutilating disease and its pathogenesis is still poorly understood. It involves the development of recurrent, painful nodules in intertriginous areas that become inflamed, form abscesses that may rupture, and develop chronic fistula tracts. The cause of hidradenitis suppurativa (HS) is thought to be multifactorial and may begin with follicular occlusion and rupture, leading to a cascade of inflammatory responses in susceptible individuals. The disease has been associated with high body mass index, smoking and genetic predisposition. There is a known association between HS and the metabolic syndrome, an association that remains after controlling for body mass index ¹. HS predominantly affects women and ethnic minorities ^{2,3} and the prevalence is thought to be as high as 2%, although embarrassment and lack of awareness may lead to an underestimate of the true burden of disease.

Although HS is a fairly common disease, relatively little is understood about its pathogenesis. Immune dysregulation is thought to play a role in disease development. Increased levels of IL-12, IL-17 and IL-23, TNF α , IL-10 and IL-1 β were found to be expressed in lesional skin of HS patients ^{4,5}. Recent studies have also identified elevated levels of IL-17 in the serum of patients with HS ⁶.

HS is associated with a significant impact on patient quality of life ⁷. Patients suffer from both the physical and psychological impact of disease. Many therapies have been used to treat HS, from topical antibiotics to oral retinoids to radical surgeries, but all have limited efficacy. Despite efforts to control disease, many patients live with chronic wounds and disability. The decision about appropriate therapy for HS, especially in the early stages, is mainly based on expert opinion, anecdotal evidence and small studies. Topical and systemic antimicrobial treatments are often used as first line therapies, although studies have repeatedly shown that the abscesses of HS are sterile or contain only normal flora. The mechanism of improvement with antimicrobials may be through alterations in the local microbiome. Significant improvement in disease has been seen with dual therapy with twice daily use of 300mg rifampicin and 300mg clindamycin ⁸, neither of which have an FDA indication for use in HS. Doxycycline is used frequently in HS, but little evidence supports this. Despite success with the above therapies, the risk of antimicrobial resistance is real, and is increased with frequent and prolonged use of these medications in HS ⁹. Teratogenic effects, gastrointestinal upset and photosensitivity with use of tetracyclines, risk for *clostridium difficile* colitis with clindamycin, and antimicrobial resistance with rifampicin highlight a need for safer and effective therapeutic options for the treatment of early HS.

For more advanced disease (Hurley stage II and III), the tumor necrosis factor inhibitor adalimumab is the only FDA approved biologic treatment for HS. It has shown promise in severe disease, but only ~50% of patients achieved a clinical response at 12 weeks, and this clinical response declined over time ¹⁰. Additionally, newer biologic therapies have been used in small numbers of patients with HS with variable results. Importantly, the cost of these

medications is considerable.

Hydroxychloroquine, initially developed as an antimalarial, has been used successfully for over 70 years in the treatment of autoimmune disease. Its mechanism of action is still poorly understood, but it has been shown to have many varied immunomodulatory properties ¹¹. Evidence suggests that hydroxychloroquine has an effect on inflammatory disease through decreasing levels of TNF α ¹² and Th-17 cytokines (including IL-6, IL-17 and IL-22)¹³. Additionally, studies have shown a beneficial effect of hydroxychloroquine on lipid metabolism and glucose ¹⁴. Patients with rheumatoid arthritis (which similarly to HS has an independent association with cardiovascular disease) who were treated with hydroxychloroquine had an overall decreased incidence of cardiovascular events ¹⁵. Hydroxychloroquine has a relatively benign safety profile, with retinopathy being the most concerning long term side effect. The retinopathy caused by hydroxychloroquine is reversible if identified early, and standard protocols for the use of this medication include yearly ophthalmologic examination.

3.0 Experimental Design and Methods

We hypothesize that treatment with hydroxychloroquine may offer a safer and effective method to control disease activity in HS. We hypothesize that the profiling inflammatory cytokines in the peripheral blood of the patients with HS may provide novel therapeutic targets for the disease. Additionally, monitoring of inflammatory cytokines before and after treatment may help to explain the mechanism by which therapies work. Over the proposed period, we intend to gather data about patient response to treatment with hydroxychloroquine and about the cytokine profile of patients with HS. Sequential patients will be assigned to hydroxychloroquine treatment. Patients will be evaluated at baseline and after 3 months of treatment for treatment response and to evaluate quality of life measures. Serum will be collected at baseline and following 3 months of treatment. Peripheral blood from patients with HS will be analyzed for levels of cytokines thought to be involved in HS and several markers of inflammation that have not yet been analyzed in this disease.

Treatment

Patients will have baseline CBC and CMP evaluation prior to initiation of therapy
Sequential patients will be assigned treatment with hydroxychloroquine 200mg BID
Treatment length will be 3 months

Evaluation of HS

Patients will be evaluated at baseline and at 3 months by:

Hurley staging:

Stage 1: solitary or multiple, isolated abscess formation without scarring or sinus tracts

Stage 2: recurrent abscesses, single or multiple widely separated lesions, with sinus tract formation

Stage 3: diffuse or broad involvement, with multiple interconnected sinus tracts and abscesses

Number of inflammatory nodules, abscesses, fistulas, scars, locations of these lesions, longest distance between 2 relevant lesions, are lesions separated by normal skin (for Sartorius scoring)

Improvement in HS lesions

Sartorius score: A statistically significant decline in Sartorius scoring between baseline and end of treatment

Evaluation of quality of life

Patients will be asked to fill out Dermatology Life Quality Index (DLQI) survey at baseline and 3 months. It is a simple, validated 10-question questionnaire. Answers to the questionnaire will be entered into a database.

For general inflammatory skin conditions a change in DLQI score of at least 4 points is considered clinically important

Serum for evaluation

Peripheral blood will be collected at baseline and after 3 months of treatment. A 10 ml red top tube of venous blood will be obtained from patients at the time of enrollment and at month 3 for banking and cytokine analysis. The red top tubes will be centrifuged, sera will be aliquoted, logged in the database and stored indefinitely at -80°C without identifiers by a technician in [name] laboratory.

Cytokine analysis

Using an inflammatory cytokine panel, levels of cytokines including L-1 β , IL-4, IL-6, IL-10, IL-17A, IL-17F, L-21, IL-22, IL-23, IL-25, IL-31, IL-33, IFN- γ , sCD40L and TNF- α will be evaluated at baseline and 3 months. Analysis will be performed at the University of Pittsburgh Cancer Institute Luminex core facility using multianalyte profiling. Levels will be compared to age, sex and BMI matched controls in our database.

Therapy may be discontinued for any of the following reasons:

Unacceptable adverse event(s),

Patient decides to withdraw from the study, or

General or specific changes in the patient's condition render the patient unacceptable for further treatment in the judgment of the investigator.

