4.0 Human Subjects

Protection of Human Subjects

Human Subjects Involvement, Characteristics, and Design. The racial, gender and ethnic characteristics of the proposed subject population will reflect the demographics of Pittsburgh and the surrounding area and/or the patient population of the UPMC Health Systems. We shall attempt to recruit subjects in respective proportions to these demographics. No exclusion criteria will be based on race, ethnicity, gender, or socioeconomic status. The numbers of enrolled male to female subjects will be consistent with and reflective of the numbers of patients seen in the UPMCHS clinics and in approximate 1:1 proportion.

Sources of material.

Information on the subject's medical history will be obtained relative to the inclusion and exclusion criteria. Data collection methods will include data obtained specifically for research purposes based on the most recent office note. All records related to this research study will be stored in a locked file cabinet. The subject's identity on these records will be indicated by a case number rather than by name, and the information linking these case numbers will be kept separate from the research records.

Recruitment

Potential subjects with Hurley stage I/II hidradenitis suppurativa will be identified by the

examining physician and referred for evaluation by the principal investigator or co-investigator. Subjects will be recruited from the UPMC dermatology department clinics. Potential subjects will be evaluated by the Principal Investigator, who is also the treating physician, during a routine clinic visit prior to any screening procedures or evaluation of the medical record for research purposes. Potential subjects will be approached by physicians directly involved in their care. No “cold calling” will occur. Informed consent will be obtained on all subjects by the principal investigator prior to all screening procedures. If for any reason, a subject is excluded or resigns during the course of study, a new subject will be enrolled.

Inclusion Criteria

Enrolled HS patients must be Hurley stage I or II (defined above)

Patients may be on topical therapy only, and/or have completed non-immunosuppressive therapy at time of enrollment.

Subjects must be 18 years of age and must be able to understand the written informed consent.

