5.0 Statistical considerations

1. Sample size

- i. The study will involve 20 patients with hidradenitis suppurativa
- ii. The comparison of baseline Sartorius scores and level of the measured cytokines in peripheral blood from HS will be compared using a two-sided t test with a p value <0.05 for statistical significance.
- iii. The probability is 80% that the study will detect a difference at a two-sided 0.05 significance level if the true difference between groups is 30%.

6.0 Adverse Reaction Reporting Requirements:

This study will use the CTC version 2.0 for toxicity and Adverse Event reporting. A copy of the CTC version 2.0 can be downloaded from the CTEP home page (<http://ctep.info.nih.gov>). All appropriate treatment areas should have access to a copy of the CTC version 2.0. All Serious Adverse events that require reporting to the FDA will be reported on the FDA 3500 medwatch form found in Appendix B

- i. The following adverse reactions must be reported in the manner described below.
- ii. All adverse events which are considered to be related to the research study must be reported to the University of Pittsburgh Cancer Institute (UPCI)
- iii. All serious adverse events that meet the University of Pittsburgh Institutional Review Board's criteria for reporting can be found at (<http://irb.pitt.edu>)

	Unexpected, fatal or life threatening and associated with study drug	Unexpected, of moderate or greater severity (But not fatal or life threatening) and are associated with the research intervention	Serious, unexpected event that is associated with the study drug	Unexpected fatal or life-threatening experience which is associated with the study drug
Call to UPCI within 24 hours at [contact]	X			
Notify IRB within 24 hours	X			
Notify UPCI as soon as		X		

possible & local IRB within 10 days				
FDA notification within 15 days			X	
FDA notification within 7 days				X

An adverse reaction is considered *serious* if it is fatal or life-threatening; requires or prolongs hospitalization; produces a disability; or results in a congenital anomaly/birth defect.

An adverse reaction is considered to be of *moderate or greater severity* if it requires medical evaluation (such as additional laboratory testing) and/or medical treatment; or if it is a serious adverse reaction.

An adverse reaction is considered to be *unexpected* if it is not identified in nature, severity or frequency in the current IRB-approved research protocol or informed consent document.

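### HS cytokine levels are compared with controls matched on age, sex and BMI but not on smoking, which the protocol itself links to HS

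*Combined protocol and SAP*

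**What the plan says.** The Cytokine analysis part of section 3.0 lists 15 cytokines measured at baseline and 3 months and adds: "Levels will be compared to age, sex and BMI matched controls in our database". It gives no number of controls, matching ratio or test for that comparison.

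Section 2.0 says of HS: "The disease has been associated with high body mass index, smoking and genetic predisposition". That section is the only place where smoking appears in the plan. It is not an eligibility criterion, a required data item, a matching factor or a covariate. Section 4.0 (Sources of material) collects history relevant to the eligibility criteria and says: "Data collection methods will include data obtained specifically for research purposes based on the most recent office note". Smoking status may therefore be obtainable, but nothing requires it.

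Section 5.0 says the "level of the measured cytokines in peripheral blood from HS will be compared using a two-sided t test" at the two-sided 0.05 level, and names no covariate. It is unclear whether this test covers the control comparison. The same sentence deals with Sartorius scores, which controls would not be expected to have, yet the power statement speaks of a difference between groups.

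The purpose of the cytokine work is given in section 1.0 ("To identify biomarkers as possible therapeutic targets for the treatment of HS") and in section 3.0, which expects that "profiling inflammatory cytokines in the peripheral blood of the patients with HS may provide novel therapeutic targets for the disease".

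**The concern.** Matching on BMI shows that the plan wants a factor linked to HS balanced between patients and controls. The sentence in section 2.0 that links BMI to HS links smoking to it as well, and smoking is left free. If patients smoke more often than the database controls, and smoking moves a cytokine, that cytokine will differ between the groups even if HS has no effect on it.

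This comparison is the only one in the plan that separates HS from non-HS levels, so it bears directly on the biomarker aim. A smoking-related difference could be read as a candidate HS target. Enlarging either group would not remove the bias; it would make a false signal more likely to reach significance.

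**Working it through.** **1. The plan's own figure.** Section 5.0 states 80% power for a 30% difference at two-sided 0.05. It cannot be reproduced, because neither an SD nor a control-group size is given. Solving backwards for 20 v 20 with the noncentral t gives a standardised difference of 0.909, hence an SD of 30% / 0.909 = 33% of the reference mean. The smoking concern does not depend on this figure; it is used only in step 6.

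**2. Inputs.** From the documents: 20 patients, two-sided 0.05, a t test, and matching on age, sex and BMI. Assumed: 20 controls; a smoking-prevalence gap (patients minus controls) of 10 to 50 points; a smoker-minus-non-smoker difference of 0, 0.3, 0.5 or 0.8 SD in a cytokine; and no true HS effect.

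**3. Bias.** Bias in SD units = prevalence gap × smoking effect. The smallest non-zero value is 0.10 × 0.3 = 0.03 SD and the largest is 0.50 × 0.8 = 0.40 SD.

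**4. False-positive rate per cytokine, two-sample t test.** With 38 degrees of freedom, the noncentrality is bias / √(1/20 + 1/20). For the largest bias this is 0.40 / 0.3162 = 1.265, which gives a rejection probability of 23.4%. The full grid is:

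| Gap (points) | 0 SD | 0.3 SD | 0.5 SD | 0.8 SD |
|---|---|---|---|---|
| 10 | 5.0% | 5.1% | 5.3% | 5.7% |
| 20 | 5.0% | 5.4% | 6.1% | 7.8% |
| 30 | 5.0% | 5.9% | 7.5% | 11.5% |
| 40 | 5.0% | 6.6% | 9.5% | 16.7% |
| 50 | 5.0% | 7.5% | 12.0% | 23.4% |

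Over the 15 cells with a non-zero effect, the median is 7.5% and 11 are below 10%.

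*Paired version.* If the controls are analysed as 20 matched pairs, the noncentrality is √20 × bias / √(2(1 − ρ)), with 19 degrees of freedom. The range is 5.1% to 22.5% at within-pair correlation ρ = 0, and 5.1% to 26.9% at ρ = 0.2.

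*Sample size does not help.* At a bias of 0.20 SD the rate rises from 9.5% (20 v 20) to 16.8% (50 v 50) and 29.1% (100 v 100).

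**5. Effect of adjusting.** Simulation with 40,000 runs per cell, within-stratum SD 1, 20% of controls smoking, 30% to 70% of patients smoking, and no true HS difference; smoking effects of 0.3 to 0.8 SD except where zero is stated:

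- Unadjusted t test: 4.9% to 5.1% at zero smoking effect; 5.1% to 21.6% at 0.3 to 0.8 SD. The top value is below 23.4% because smoking adds to the total SD in this model.
- Linear model with smoking as a covariate: 4.9% to 5.3%.
- The same model with 20% of smokers recorded as non-smokers: 4.8% to 7.3%.

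**6. Price of adjusting.** The variance of the HS-versus-control estimate is multiplied by 1.02, 1.05, 1.11, 1.20 and 1.34 at gaps of 10, 20, 30, 40 and 50 points. At the extreme, the standardised difference of 0.909 becomes 0.909 / √1.34 = 0.785, and power falls from 80% to about 68% (37 degrees of freedom).

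**The case against.** The strongest objection is that confounding needs two links and the documents supply one. They tie smoking to HS but do not say that smoking changes any of the 15 cytokines, and with zero effect the error rate is 5%. This stands as a limit on size: the figures illustrate what could happen and are not evidence of harm. It does not remove the design point, because smoking is left uncontrolled although the protocol itself names it as associated with HS.

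Second, the t test in section 5.0 may not be meant for the control comparison, so the error rates may describe a test nobody plans to run. That ambiguity is real. It does not rescue the plan: if the test applies, it is unadjusted; if it does not, the control comparison has no stated analysis. A purely descriptive difference would carry the same bias of 0.03 to 0.40 SD.

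Third, smoking is not the only unmatched factor. Section 2.0 also names genetic predisposition and ethnic minorities, and adds: "There is a known association between HS and the metabolic syndrome, an association that remains after controlling for body mass index". BMI matching therefore cannot be assumed to deal with metabolic syndrome. This is correct. Smoking is singled out because one question can record it; the others would remain as limitations.

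Fourth, multiplicity may matter more. Fifteen tests at 0.05, if independent, give a 1 − 0.95^15 = 54% chance of at least one false positive with no smoking effect at all. That is fair as a matter of proportion, but correcting for multiplicity would not remove a systematic difference between the groups.

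Finally, the adjusted rates are favourable partly because the simulated data follow the additive, binary-smoking model that was then fitted. That also stands. The run with misrecorded smokers shows that some bias can survive adjustment.

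**Conclusion.** The concern holds, as a low-priority improvement. The matching set omits a factor that the protocol places beside BMI, and nothing else in the plan controls it. Neither the size nor the direction of any bias can be known from the documents. Under the assumed ranges the inflation is modest in most scenarios; the 23.4% at the top needs a 50-point prevalence gap and a 0.8 SD smoking effect together.

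The consequence is confined to the HS-versus-control comparison and to any therapeutic target inferred from it. Sartorius score, DLQI and the change in cytokines within patients do not use the controls and are not affected.

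**What to change.** Record each patient's current smoking status at enrollment, from the office note or with one question, and take it from the database for the controls. Before any cytokine result is seen, choose one of two options:

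1. Add current smoking status to the matching factors in the Cytokine analysis part of section 3.0.
2. If the control pool is too small for that, state in section 5.0 that the HS-versus-control difference is estimated by a linear model of cytokine level on case status, with current smoking as a covariate. The text should also say how the matching on age, sex and BMI is handled in that model.

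If the database does not hold smoking status, report the comparison as descriptive and name smoking as an uncontrolled confounder wherever possible targets are discussed. In every case, list the other unmatched factors from section 2.0 as limitations. The within-patient cytokine analysis needs no change.

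The cost is one data item per patient, one lookup per control, and one matching factor or model term. Matching shrinks the pool of eligible controls. Adjustment uses one degree of freedom and, under the assumptions above, raises the variance of the estimate by about 2% to 34%. Under-recorded smoking would leave some bias.

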4.0 Human Subjects

Protection of Human Subjects

Human Subjects Involvement, Characteristics, and Design. The racial, gender and ethnic characteristics of the proposed subject population will reflect the demographics of Pittsburgh and the surrounding area and/or the patient population of the UPMC Health Systems. We shall attempt to recruit subjects in respective proportions to these demographics. No exclusion criteria will be based on race, ethnicity, gender, or socioeconomic status. The numbers of enrolled male to female subjects will be consistent with and reflective of the numbers of patients seen in the UPMCHS clinics and in approximate 1:1 proportion.

Sources of material.

Information on the subject's medical history will be obtained relative to the inclusion and exclusion criteria. Data collection methods will include data obtained specifically for research purposes based on the most recent office note. All records related to this research study will be stored in a locked file cabinet. The subject's identity on these records will be indicated by a case number rather than by name, and the information linking these case numbers will be kept separate from the research records.

Recruitment

Potential subjects with Hurley stage I/II hidradenitis suppurativa will be identified by the

examining physician and referred for evaluation by the principal investigator or co-investigator. Subjects will be recruited from the UPMC dermatology department clinics. Potential subjects will be evaluated by the Principal Investigator, who is also the treating physician, during a routine clinic visit prior to any screening procedures or evaluation of the medical record for research purposes. Potential subjects will be approached by physicians directly involved in their care. No “cold calling” will occur. Informed consent will be obtained on all subjects by the principal investigator prior to all screening procedures. If for any reason, a subject is excluded or resigns during the course of study, a new subject will be enrolled.

Inclusion Criteria

Enrolled HS patients must be Hurley stage I or II (defined above)

Patients may be on topical therapy only, and/or have completed non-immunosuppressive therapy at time of enrollment.

Subjects must be 18 years of age and must be able to understand the written informed consent.

No evidence of active infection, regardless of the degree of severity or localization. Subjects with active infections (whether or not they require antibiotic therapy) may be eligible after complete resolution of the infection. Subjects on antibiotic therapy must be off antibiotics for at least 7 days before beginning treatment.

Exclusion criteria

Subjects currently on systemic immunosuppression are ineligible

Subjects under 18 years of age

Due to small risk of retinopathy, hepatic disease, psoriasis exacerbation, exacerbation of porphyria cutanea tarda (PCT) in patients treated with hydroxychloroquine, subjects with known retinal disease, hepatic disease, psoriasis and PCT will be excluded

Due to potential fetal risk with use of hydroxychloroquine, pregnant patients or those planning to become pregnant will be excluded

Risks to the subjects:

- i. The risks of the study are minimal and are related drug therapy and to obtaining the blood samples needed for our analysis.
 1. Physical.
 - a) Small likelihood of drug toxicity. Hydroxychloroquine has been used for many years and is known to have a mild side effect profile.
 - b) Small likelihood of infection or bleeding. Risks minimized by proper protective equipment and hygiene
 2. Psychological. There is a small likelihood of low psychological risk if participants are upset by request to be involved in the study

7. Benefits

- i. Benefits may accrue to patients with HS. Benefits may accrue to study subjects who participate through greater awareness leading to greater individual and community empowerment, enhanced knowledge of community assets as well as health concerns and needs, and enhanced skills related to performance of duties as study subjects. Outside of participants in research, all community members may also benefit from enhanced trust and reciprocity within the community.

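### Topical therapy is allowed at entry with no stable-use period before baseline, so if some patients started one recently, its later benefit would be read as hydroxychloroquine response

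*Combined protocol and SAP*

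**What the plan says.** All rules on earlier or concurrent treatment are in section 4.0 Human Subjects.

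- Inclusion criteria: "Patients may be on topical therapy only, and/or have completed non-immunosuppressive therapy at time of enrollment". No minimum duration, stable-use period or run-in is attached.
- Within the criterion on active infection: "Subjects on antibiotic therapy must be off antibiotics for at least 7 days before beginning treatment". This is the only prior-treatment rule with a time limit. It does not say whether topical antibiotics count.
- Exclusion criteria: "Subjects currently on systemic immunosuppression are ineligible". Topicals are not mentioned.
- Recruitment: the treating physician, who is also the principal investigator, evaluates candidates "during a routine clinic visit prior to any screening procedures".

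Section 3.0 sets the design and the efficacy criterion.

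- Allocation: "Sequential patients will be assigned to hydroxychloroquine treatment". There is no concurrent comparison group for the clinical outcomes.
- Duration: "Treatment length will be 3 months".
- Improvement in lesions: "A statistically significant decline in Sartorius scoring between baseline and end of treatment".
- External controls appear only under cytokine analysis: "Levels will be compared to age, sex and BMI matched controls in our database".

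No section asks for the start date of a topical or says how topical use enters the analysis.

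**The concern.** In a one-arm before-and-after comparison, everything that moves the score between the two visits is credited to the study drug. A topical in long, steady use has largely had its effect by baseline and adds little to the change. A topical started days before baseline has most of its effect still to come, and that effect falls inside the 3-month window.

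Such a patient can meet the topical-therapy criterion and continue the same product to month 3 without any change. A rule on treatments started or altered during the study would therefore not identify the patient. The remedy has to act before baseline, or the start date has to be known.

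The setting makes this possible. Section 2.0 describes topical antimicrobials as common first-line treatment, entry is limited to Hurley stage I or II, and recruitment runs through ordinary dermatology visits. At stake is a result that favours hydroxychloroquine, on the Sartorius score and on the DLQI, for a reason unrelated to the drug.

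**Working it through.** **The plan's own figure.** Section 5.0 gives 20 patients, a two-sided t test at 0.05, 80% power and a true difference of 30%. It gives no SD, so the 80% cannot be verified. It can only be solved for the SD that would produce it. For a paired t test with n = 20, noncentral-t power reaches 80% at a standardised change of 0.660, so

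SD of change = 0.30 / 0.660 = 0.454 of the baseline mean.

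The section speaks of a difference between groups. Read as two independent groups, the implied SD is 0.330 (20 vs 20) or 0.226 (10 vs 10). The paired reading is used below because the efficacy criterion is a within-patient decline. That choice is an assumption.

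**Assumed inputs (in neither section 4.0 nor 5.0).**
- f, the share of patients who started a topical shortly before baseline: 10%, 25%, 50%.
- e, the fall in score from that topical after baseline, as a fraction of the baseline mean: 10%, 20%, 30%.
- Hydroxychloroquine has no effect, and nothing else shifts the mean.

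**Formulas.**
- Spurious mean fall = f × e.
- SD of change = √(0.454² + f(1 − f)e²).
- Noncentrality = (f × e / SD) × √20, with 19 degrees of freedom.
- Chance of a significant decline = upper tail beyond t = 2.093. With no shift this is 2.5%.

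**One cell in full (f = 25%, e = 20%).** Spurious fall = 0.25 × 0.20 = 0.05. SD = √(0.2063 + 0.25 × 0.75 × 0.04) = √0.2138 = 0.462. Noncentrality = (0.05 / 0.462) × 4.472 = 0.484. Chance = 6.7%.

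| Recent starters (f) | Topical effect (e) | Spurious fall, % of baseline | Chance of a significant decline |
|---|---|---|---|
| 0% | any | 0 | 2.5% |
| 10% | 10% | 1.0 | 3.1% |
| 10% | 20% | 2.0 | 3.8% |
| 10% | 30% | 3.0 | 4.6% |
| 25% | 10% | 2.5 | 4.2% |
| 25% | 20% | 5.0 | 6.7% |
| 25% | 30% | 7.5 | 9.9% |
| 50% | 10% | 5.0 | 6.7% |
| 50% | 20% | 10.0 | 14.8% |
| 50% | 30% | 15.0 | 26.5% |

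Against the planned 30% difference, the spurious fall runs from 1/30 = 3% to 15/30 = 50%. A smaller SD would raise the chances in the last column and a larger one would lower them.

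**Power of an analysis without recent starters.** With a true 30% fall and SD 0.454, dropping 25% of 20 leaves 15 patients and a noncentrality of 0.660 × √15 = 2.56, for power of about 66%. Dropping 50% leaves 10 patients and a noncentrality of 0.660 × √10 = 2.09, for power of about 46%.

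**The case against.** The strongest objection is the 7-day antibiotic rule. Its wording is not confined to systemic antibiotics, and antimicrobials are the only topical class the background section names for this disease. On that reading, a patient who had just begun a topical antibiotic would have to stop it before study treatment and could not be the patient described. This stands in part. The rule sits inside the infection criterion, does not mention topicals, and on the wide reading would conflict with the allowance of topical therapy. It leaves other topicals untouched on any reading. The two criteria must be reconciled; which reading is intended is for the sponsor to say.

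Second, nothing in the plan says that topicals are prescribed at the recruiting visit or that baseline scoring follows soon after a new prescription. That stands: the bias arises only if recent starters are enrolled.

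Third, the upper rows of the table are generous. An effect of 30% gives a topical the whole planned difference, while section 2.0 calls the efficacy of existing therapies limited, topical antibiotics included. The low rows, at about 3-5%, are small departures from 2.5% and belong in the range.

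Fourth, patients who have just completed another therapy may lose its benefit during follow-up, which would act against the drug. The net direction of bias from all prior treatment is therefore unknown; the direction stated here concerns beneficial new topicals only.

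Fifth, natural fluctuation and regression to the mean also enter an uncontrolled before-and-after change, and a stability rule leaves them in place. True, but they do not make this avoidable source harmless, since evaluating efficacy is a stated aim of the pilot.

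**Conclusion.** The point holds in a conditional form. The plan admits topical therapy with no stable-use period, no other section supplies one, and the efficacy criterion has no means of separating a new topical's effect from the drug's. If recent starters are enrolled and their topical works, the result is biased towards hydroxychloroquine.

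The size is unknown. Under the paired reading, an SD of change of 0.454 and an inactive drug, the chance of a significant decline lies between about 3% and 27% over the assumed ranges, against 2.5% nominally. These figures show how the bias scales and do not estimate what will happen.

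A reader might infer that topical effects will certainly be counted as drug response, or that the false-positive chance is at least 7%. The documents support neither: they do not show that anyone will have started a topical recently, they give no topical effect, and the 7-day rule may remove some such patients. Priority is minor to moderate.

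**What to change.** 1. Add to the inclusion criterion on topical therapy that any topical regimen has been unchanged for a stated period before the baseline score. The sponsor sets the length.
2. State whether the 7-day antibiotic rule applies to topical antibiotics, so that it and the topical allowance agree.
3. Record the start date of each topical at baseline. If these dates are not collected prospectively, the question may be impossible to examine afterwards.
4. If the criterion is not changed, prespecify a supportive Sartorius analysis that omits patients who started a topical within the stated period. Report it as an estimate with its confidence interval and not as a second significance test, because its power would be reduced (about 66% with 15 patients, 46% with 10).

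The cost is one line in the criteria, one clarification and one baseline field. The downside is that some patients are deferred until their regimen is stable, and the more common recent starts are, the more patients this affects. Without the criterion, the cost is one extra supportive analysis with limited precision.
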